### **12.4 *Correlate tumor response to Vitamin D3 serum levels, and VDR status*** (Secondary

Objective)

See Section 10.0 for description of how the blood samples will be handled and analyzed.

## **13.0 RECORDS TO BE KEPT / REGULATORY CONSIDERATIONS**

Adverse event lists, guidelines, and instructions for AE reporting can be found in Section 8.0 (Adverse Events: List and Reporting Requirements).

### **13.1 Data Reporting**

The OnCore Database will be utilized, as required by the Case Comprehensive Cancer Center, to provide data collection for both accrual entry and trial data management. OnCore is a Clinical Trials Management System housed on secure servers maintained at Case Western Reserve University. OnCore properly used is compliant with Title 21 CFR Part 11. Access to data through OnCore is restricted by user accounts and assigned roles. Once logged into the OnCore system with a user ID and password, OnCore defines roles for each user which limits access to appropriate data. User information and password can be obtained by contacting the OnCore Administrator at [[contact]](mailto:[contact]).

OnCore is designed with the capability for study setup, activation, tracking, reporting, data monitoring and review, and eligibility verification. This study will utilize electronic Case Report Form completion in the OnCore database. A calendar of events and required forms are available in OnCore.

### **13.2 Regulatory Considerations**

The study will be conducted in compliance with ICH guidelines and with all applicable federal (including 21 CFR parts 56 & 50), state or local laws.

#### ***13.2.1 Written Informed consent***

Provision of written informed consent must be obtained prior to any study-related procedures. The Principal Investigator will ensure that the subject is given full and adequate oral and written information about the nature, purpose, possible risks and benefits of the study as well as the subject's financial responsibility. Subjects must also be notified that they are free to discontinue from the study at any time. The subject should be given the opportunity to ask questions and allowed time to consider the information provided.

The original, signed written Informed Consent Form must be kept with the Research Chart in conformance with the institution's standard operating procedures. A copy of the signed written Informed Consent Form must be given to the subject.

#### ***13.2.2 Subject Data Protection***

In accordance with the Health Information Portability and Accountability Act (HIPAA), a subject must sign an authorization to release medical information to the sponsor and/or allow the sponsor, a regulatory authority, or Institutional Review Board access to subject's medical information that includes all hospital records relevant to the study, including subjects' medical history.

#### ***13.2.3 Accessing Electronic Medical Records for University Hospitals Health System:***

*Not applicable.*

#### **13.2.4 Retention of records**

The Principal Investigator of The Case Comprehensive Cancer Center supervises the retention of all documentation of adverse events, case report forms, source documents, records of study drug receipt and dispensation, and all IRB correspondence for as long as needed to comply with national and international regulations and the institution in which the study will be conducted, or for the period specified by the sponsor, whichever is longer. No records will be destroyed until the Principal Investigator confirms destruction is permitted.

#### **13.2.5 Audits and inspections**

Authorized representatives of the sponsor, a regulatory authority, an Independent Ethics Committee (IEC) or an Institutional Review Board (IRB) may visit the Center to perform audits or inspections, including source data verification. The purpose of an audit or inspection is to systematically and independently examine all study-related activities and documents to determine whether these activities were conducted, and data were recorded, analysed, and accurately reported according to the protocol, Good Clinical Practice (GCP), guidelines of the International Conference on Harmonization (ICH), and any applicable regulatory requirements.

#### **13.2.6 Data Safety and Monitoring Plan**

This protocol will adhere to the policies of the Case Comprehensive Cancer Center Data and Safety Monitoring Plan in accordance with NCI regulations.

## **14.0 STATISTICAL CONSIDERATIONS**

### **Primary objective:**

#### **Statistical Analysis**

Patients receiving neoadjuvant D3/PDT will be first matched to control patients who received PDT alone (in our previous study, IRB 16-1615) in a 1:1 ratio based upon the baseline 25OH-D3 values. The 25OH-D3 values will have three strata: normal blood levels, intermediate, and low. The matching will also be stratified, i.e., normal level patients who received D3/PDT will be matched to normal level patients who received PDT, and so on. Within each stratum, the matching will be done with the optimal algorithm by considering 25OH-D3 as a continuous variable. The outcome,  $\Delta C$ , (% decrease in lesion number), will then be compared between the two matched groups using the paired t-test. Statistical significance will be established at a two-sided p-value  $< 0.05$ . As a sensitivity analysis, a linear mixed-effect model will be used to adjust the comparison for baseline 25OH-D3 values. A random two-way ANOVA model will also be used to include therapy, D3 strata and their interactions in the model to examine whether the treatment effect differs by strata.

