### 3.0 STUDY DESIGN

#### 3.1 Study Design Protocol

This is a non-randomized interventional trial, in which the study group will be compared to a baseline cohort of patients from a previous study (IRB 16-1615) who received the same regimen of PDT, but without any Vit D. Our protocol is shown in Fig. 5. The dose of D3 chosen for this study reflects the best currently available evidence regarding efficacy, safety, and practicality of oral D3 dosing. In our mouse studies, the human equivalent of 10,000 IU given daily for 10 d, provided better PpIX enhancement than 5,000 IU/d x 10 d, with no evident toxicity [12]. In normal mice, 3 d of daily 10,000 IU were just as good as 10 d for boosting PpIX levels in tumors; however, the 3-day regimen worked only about half as well in VD-deficient mice (prelim data; Fig. 4). Importantly however, 10 d were sufficient to restore the PpIX elevating effect in VD deficient animals (Fig. 4). Therefore, we will tailor the neoadjuvant D3 dose in this clinical trial, according to initial serum 25OH-D3 levels, to maximize convenience and safety, while testing for equivalence of therapeutic benefit. Specifically, study patients with normal VD levels will take a daily 10,000 IU D3 pill for 3-5 d, while patients with suboptimal VD levels will take the D3 pill for 10-14 d. (Ranges are given to compensate for patients possibly missing a day or two). Regarding safety, the doses of D3 that physicians use to treat VD deficiency can be remarkably high, including 5,000 IU (oral, daily, continuous), 50,000 IU (oral, twice weekly for 5 weeks), and 500,000 IU (i.m., single dose); all are reported safe and effective[34]. Our dosing regimen is well within these safe ranges.

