### **5.3 Randomization:**

There will be no randomization procedures.

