## **12.2 Methods for Evaluation of AK Response**

### **12.2.1 *Number of AK Lesions Measured from Clinic Visits and Photographic Images***

(Primary Objective)

Percent reduction of actinic keratoses at a 3-month follow-up visit will be used to evaluate the overall outcome of PDT with prior Vitamin D supplementation. This will be achieved by counting AK lesions at visit 2 and visit 3.

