#### **Secondary objectives:**

- To assess the level of PpIX accumulation in AK lesions at treatment visits, in the absence or presence of neoadjuvant D3. (fluorescence dosimetry measurements)
- To assess tolerability of the technique. (Pain scale measurements)
- To assess patient satisfaction with the technique. (Cosmetic result, and questionnaire)
- To assess D3 serum levels (in serum) and VDR status (in leukocyte DNA), and to correlate these results to clinical outcomes.

Characteristics of the above parameters will be summarized as means and standard deviations (medians and quartiles) or percentages and frequencies. We will also compare the characteristics of screened and randomized patients using appropriate two-sample comparison procedures (t-test, Chi-squared test, etc.).

Analyses of study endpoints will follow the intention-to-treat (ITT) principle. For each relevant

endpoint, we will summarize its trajectories over study visits by randomization assignment for each patient. Linear mixed-effects models will be the primary analytic tools to analyze continuous endpoints by accounting for within-patient randomization, multiple lesions from the same patient and repeated measurements over time. The models will include fixed effects of treatment and visit and multiple random effects that represent the hierarchical data structure. Similarly, generalized linear mixed-effects models will be applied to categorical endpoints (binomial data, e.g., number of lesions with CR). The analysis for time to clearance will be based on a random-frailty survival model, where lesions without CR will be considered to have clearance times censored at the end of study. Further exploratory analyses will adjust these models by controlling for important initial parameters (e.g., initial tumor size).

All analyses will be conducted using SAS 9.3 (Cary, NC). Results will not be adjusted for multiple comparisons, and statistical significance will be established with a two-sided p-value < 0.05.

**Estimate of the accrual rate:** Patients who have been scheduled to receive PDT in our noninvasive cutaneous oncology clinics will be given written information prior to their visit, including a copy of the Informed Consent (IC) that describes the purpose of the study. If the patient indicates that he/she is interested, the physician or study nurse will review the IC with the patient on the day of PDT and answer all questions. We estimate an enrollment of 1 patient each week.

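### Does the leftover intention-to-treat and randomization wording leave the primary paired comparison undefined when a Visit 3 count is missing?

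*Combined protocol and SAP*

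**What the plan says.** The primary analysis in Section 14.0 has a stated order. "Patients receiving neoadjuvant D3/PDT will be first matched to control patients who received PDT alone", one to one on baseline 25OH-D3 within strata, and the percent decrease in lesion number "will then be compared between the two matched groups using the paired t-test". Section 12.2.1 defines how that outcome is obtained: "This will be achieved by counting AK lesions at visit 2 and visit 3".

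Later in Section 14.0, after the list of secondary objectives (PpIX, tolerability, satisfaction, and vitamin D and VDR correlations), the text states: "Analyses of study endpoints will follow the intention-to-treat (ITT) principle". It adds that for each relevant endpoint "we will summarize its trajectories over study visits by randomization assignment for each patient", and that "Linear mixed-effects models will be the primary analytic tools to analyze continuous endpoints by accounting for within-patient randomization".

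On design, Section 3.1 says "This is a non-randomized interventional trial" and Section 5.3 says "There will be no randomization procedures". Section 3.2 asks for 30 patients to complete the study, Section 3.3 allows a withdrawn subject to be replaced, and the sample size text gives a recruitment aim of 35.

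**The concern.** A paired t-test on percent decrease cannot use a patient who had PDT but has no Visit 3 count. The pair is lost. The intention-to-treat sentence speaks of study endpoints in general, and a mixed model fitted to counts by visit would keep a patient seen only at Visit 2. On that reading the two parts of Section 14.0 treat the same patient differently. If the sentence reaches only the secondary objectives, the primary test has no missing-data rule at all. In either case the intention-to-treat text cannot be applied literally, because it refers to a randomization that Sections 3.1 and 5.3 exclude.

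The design gives this some weight. The control group already exists, so the choice of who enters the primary test could be made with control outcomes known. Section 3.3 does not say whether a patient replaced after PDT is still analysed. If patients who do not return differ in response from those who do, and controls do not show the same pattern, the completer difference is biased.

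**Working it through.** **1. Do the two parts of Section 14.0 conflict?** The primary outcome is one number per patient, built from Visits 2 and 3. Neither part says what happens to a patient without the second count. The conflict arises only if the later mixed model is applied to the primary endpoint and is also fitted to raw counts by visit. Any model of percent decrease itself, including the mixed model that Section 14.0 names as a sensitivity analysis for the primary comparison, omits that patient as the t-test does. The later text follows the list of secondary aims, and the earlier text already names the primary test. The consistent reading is a complete-pair paired t-test.

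**2. Reproducing the sample size.** Inputs from Section 14.0: means 70% and 90%, common SD 24, correlation 0.1, two-sided alpha 0.05.

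- SD of paired differences = 24 × √(2 × (1 − 0.1)) = 32.2.
- Noncentral t power for a 20-point difference: 29 pairs 89.8%, 30 pairs 90.8%, 35 pairs 94.6%.

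The stated 30 patients at 90% power is therefore a count of complete pairs. With 35 treated and five without a Visit 3 count (5/35 = 14.3%), 30 pairs remain. With 25 pairs, power is 84.6%.

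**3. Does the order of matching and dropping matter?** Suppose one order leaves 25 pairs and the other 30. Simulating 30 paired differences (SD 32.2) and testing the first 25 and then all 30, with no matching and no bias, gives verdicts that differ in about 8-9% of trials at a true 20 points and about 15% at 12 points. At least one of the two is significant in about 7% of trials when there is no effect. A full simulation of the two matching orders, with an assumed control pool of 40-100 and 14% of controls also missing, gives almost the same figures: 8-9%, 14-16% and about 7%. The disagreement comes from testing 25 rather than 30 pairs. The 7% applies only if someone reports whichever result is significant.

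**4. Selective loss.** The documents give no loss rate, so five of 35 is an assumption, with controls taken as unaffected.

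- If the five lost patients average 50% clearance against a true mean of 70%, the completer mean is (70 × 35 − 5 × 50)/30 = 73.3. The shift is 3.3 points and false positives are 8.5%.
- If loss is related to outcome with correlation 0.2 or 0.3, the shift is 1.2 or 1.8 points, and false positives are 5.5% or 5.9%.
- If good responders are the ones who stay away (correlation −0.3), the shift is −1.8 points, against vitamin D.
- If exactly the five worst responders are lost, the shift is 6-7 points and false positives are 17-21%. This is the extreme.

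**5. Tipping point.** At 30 pairs the smallest significant difference is 2.045 × 32.2/√30 = 12.0 points. Now add five missing pairs with mean m and the same within-set SD to 30 observed pairs with mean d, and retest on 35:

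- mean = (30d + 5m)/35
- variance = [33 × 32.2² + (30 × 5/35)(d − m)²]/34

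| Observed difference d (30 pairs) | Mean m of the five missing pairs at which significance is lost |
|---|---|
| 12.84 | 0 |
| 15 (p = 0.016) | about −11 |
| 20 (p = 0.002) | about −32 |

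**The case for a change.** The best case for a change is that the gap is real and cheap to close. Section 14.0 has no analysis set for the primary endpoint, no rule for a broken pair, and intention-to-treat text that cannot be applied literally. The heading over that text is not decisive, because the same block models lesion clearance and names the software for all analyses. The plan also does not exclude any handling rule, and rules can differ sharply. With an assumed 10% missing in the vitamin D group and 35 treated, the expected difference is 20 points if pairs are dropped (power 92.5%, loss unrelated to outcome) but 11 points if missing values are set to zero clearance in that group only (power 33.2%).

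What stands is that the rule is unwritten and the randomization terms are wrong. The range just quoted depends on a rule that nobody would adopt for a matched comparison without saying so, since it penalises one group only. The terms mislead nobody about the design: Sections 3.1 and 5.3 are explicit, and Section 9.2 carries a similar leftover about placebo in a randomized study. An analyst would read assignment as cohort. Section 3.3 leaves the status of a replaced patient open, but an analyst would ordinarily report withdrawals and replacements.

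The remedies would also gain little. Imputation in about 35 patients is imprecise and does not correct loss that depends on outcome. Extraction from the medical record at the 3-month follow-up is already planned under Procedure (C) in Section 10.

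**Conclusion.** No change follows. This is missing detail that an analyst fills sensibly, together with a clerical residue of randomization language. The plan names the primary test, its matching and its order, and following it yields complete pairs. The design is sized for that: 30 completers, 35 recruited, replacement allowed, and 90.8% power at 30 pairs.

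The remaining exposure is modest and of unknown direction. At loss-outcome correlations of 0.2-0.3, false positives rise from 5% to 5.5-5.9%, and equal loss in both cohorts would cancel. A 20-point result is robust. A result just above 12 points would be fragile, and a reader should look at how many counts are missing before relying on it. These figures rest on the plan's SD and correlation and on an assumed loss of five of 35. Actual loss may be smaller, since Visit 3 is mandatory and coincides with routine follow-up. The sample size is not in error.

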#### **Sample size estimates:**

We estimated the variance within our actinic keratosis (AK) study population by using data from our prior pilot studies that examined PDT for AK of the face and scalp [10]. The mean clearance of the AK lesion counts was 70%, with a SD of 24% (n=30) three months after PDT. We hypothesize that the clearance rate with neoadjuvant D3 will be 90%. For this effect size, we would need 30 patients to achieve a power of 90% (assuming a common SD of 24%, two-sided alpha=0.05, 0.1 correlation). As an enrollment estimate, we aim to recruit 35 patients.

#### **Secondary objectives:**

- To assess the level of PpIX accumulation in AK lesions at treatment visits, in the absence or presence of neoadjuvant D3. (fluorescence dosimetry measurements)
- To assess tolerability of the technique. (Pain scale measurements)
- To assess patient satisfaction with the technique. (Cosmetic result, and questionnaire)
- To assess D3 serum levels (in serum) and VDR status (in leukocyte DNA), and to correlate these results to clinical outcomes.

Characteristics of the above parameters will be summarized as means and standard deviations (medians and quartiles) or percentages and frequencies. We will also compare the characteristics of screened and randomized patients using appropriate two-sample comparison procedures (t-test, Chi-squared test, etc.).

Analyses of study endpoints will follow the intention-to-treat (ITT) principle. For each relevant

endpoint, we will summarize its trajectories over study visits by randomization assignment for each patient. Linear mixed-effects models will be the primary analytic tools to analyze continuous endpoints by accounting for within-patient randomization, multiple lesions from the same patient and repeated measurements over time. The models will include fixed effects of treatment and visit and multiple random effects that represent the hierarchical data structure. Similarly, generalized linear mixed-effects models will be applied to categorical endpoints (binomial data, e.g., number of lesions with CR). The analysis for time to clearance will be based on a random-frailty survival model, where lesions without CR will be considered to have clearance times censored at the end of study. Further exploratory analyses will adjust these models by controlling for important initial parameters (e.g., initial tumor size).

All analyses will be conducted using SAS 9.3 (Cary, NC). Results will not be adjusted for multiple comparisons, and statistical significance will be established with a two-sided p-value < 0.05.

**Estimate of the accrual rate:** Patients who have been scheduled to receive PDT in our noninvasive cutaneous oncology clinics will be given written information prior to their visit, including a copy of the Informed Consent (IC) that describes the purpose of the study. If the patient indicates that he/she is interested, the physician or study nurse will review the IC with the patient on the day of PDT and answer all questions. We estimate an enrollment of 1 patient each week.

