Other preliminary data using **oral D3 supplementation** in mice with skin tumors (**Fig. 4**) indicate that VD-deficient individuals may be significantly less responsive to ALA-PDT than subjects with normal VD levels. In tumor-bearing mice that were rendered VD deficient on a D3 free diet (as verified by 25OH-D3 serum assay), the administration of ALA to induce PpIX synthesis in tumors produced only 50% of the usual amount of PpIX (Fig. 4; 1st and 2nd bars). In the VD deficient mice, a short course of neoadjuvant D3 (10,000 IU/d of a human equivalent dose) for 3 d failed to boost intratumoral PpIX production to the same extent as in VD replete mice (Fig. 4; 3rd and 4th bars). However, if the course of neoadjuvant D3 was lengthened to 10 d, then both the VD-deficient and VD-normal mice experienced the same benefit, in terms of similar increases in PpIX levels (Fig. 4; 5th and 6th bars). These data inform our selection of conditions for D3 supplementation in the clinical trials. We will give a neoadjuvant D3 boost to patients with AKs, prior to ALA-PDT, that is tailored to their initial baseline VD levels. Thus, patients with normal VD levels will take D3 pills for 5 days, whereas patients with low VD levels will take D3 for 14 d.

**Figure 4.** Effect of VD deficiency upon production of PpIX photosensitizer in skin tumors. *Nude* mice were made VD deficient by feeding for 4-weeks with a no-D3 diet (gray bars); controls ate a normal diet (white bars). Serum levels of 25OH-D3 in the VD-def mice dropped to  $3 \pm 2$  ng/mL, compared to  $25 \pm 4$  ng/mL in normal mice (data not shown). SCC cells (A431) were implanted s.c. and allowed to grow for 10 d. The neoadjuvant D3 regimen (oral D3, using a 10x high D3 diet) was given for 3 d or for 10 d, immediately prior to giving ALA by i.p. injection. Four hours later, tumors were harvested for PpIX analysis by confocal fluorescence microscopy of frozen tumor sections.

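### The model for PpIX does not say whether it uses the 25OH-D3-matched set, and it has no 25OH-D3 or matched-pair term

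*Combined protocol and SAP*

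**What the plan says.** The first secondary objective in Section 14.0 is a comparison between cohorts: "To assess the level of PpIX accumulation in AK lesions at treatment visits, in the absence or presence of neoadjuvant D3". For continuous endpoints of this kind the section names linear mixed-effects models: "The models will include fixed effects of treatment and visit and multiple random effects that represent the hierarchical data structure". Covariates come later and only as exploration: "Further exploratory analyses will adjust these models by controlling for important initial parameters (e.g., initial tumor size", the one example being lesion size.

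The primary endpoint, percent decrease in lesion number, is treated differently. Section 14.0 matches 1:1 on 25OH-D3 within three strata, uses a paired t-test, and adds: "As a sensitivity analysis, a linear mixed-effect model will be used to adjust the comparison for baseline 25OH-D3 values". An ANOVA with therapy, stratum and their interaction follows.

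Matching is not confined to that endpoint. Section 1.7 says that every patient will be matched on baseline calcidiol. Section 2.1 repeats this under Aim 1, directly above Subaim 1a, which is the PpIX question.

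On the link between vitamin D status and PpIX, Section 1.5 reports that giving ALA to deficient mice "produced only 50% of the usual amount of PpIX". After the longer D3 course, "then both the VD-deficient and VD-normal mice experienced the same benefit, in terms of similar increases in PpIX levels". Section 3.1 draws the design consequence: "we will tailor the neoadjuvant D3 dose in this clinical trial, according to initial serum 25OH-D3 levels".

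**The concern.** PpIX is the mechanism in the primary hypothesis (Section 2.0), and it is the endpoint for which the protocol has direct evidence of dependence on vitamin D status. Section 10.1 asks whether 25OH-D3 affects PpIX, yet no specified PpIX model contains it. The cohorts are non-randomized and come from different studies, so an equal share of deficient patients cannot be taken for granted.

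The paragraph that should settle the matter does not fit this trial. It refers to randomization assignment and within-patient randomization, while Section 5.3 says there is none. It also includes a visit effect, while the calendar in Section 11.6 measures PpIX at one visit only. An analyst following it literally would fit treatment with patient and lesion random effects, without 25OH-D3 or the pair, on a set of controls that the text leaves undefined. What is at stake is either a biased contrast or a less powerful one, depending on which controls are used.

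**Working it through.** **The plan's own figure.** Section 14.0 gives no SD, effect size or power for PpIX. Its only sample-size figure is for clearance. SD of paired differences = 24 × √(2 × (1 − 0.1)) = 32.2; with a difference of 20 points and two-sided alpha 0.05, the noncentral t gives n = 30 with power 90.8%. The stated 30 patients and 90% reproduce.

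**Inputs for PpIX.**
- From the documents: 30 patients and 1:1 matching, so 30 per group. Deficient mice given no D3 reach 0.5 of usual PpIX, so the drop is h = 0.5 in units where normal PpIX = 1. Those mice were at about 3 versus 25 ng/mL (legend to Figure 4).
- Assumed, because the documents give nothing: h = 0.25 as a milder case; within-stratum SD of patient means, 0.3 to 0.5; deficient shares, 20% to 50%; a true D3 gain of 0.25.

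**Case A: PpIX analysed outside the matched set.** Standardized to the D3 cohort, bias = h × (pC − pT), where pC and pT are the deficient shares in controls and D3 patients. This holds whatever PpIX is under D3.

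| pC / pT | Bias, h = 0.5 | % of control mean | Bias, h = 0.25 | % of control mean |
|---|---|---|---|---|
| 40% / 30% | +0.05 | +6.3 | +0.025 | +2.8 |
| 50% / 30% | +0.10 | +13.3 | +0.05 | +5.7 |
| 50% / 20% | +0.15 | +20.0 | +0.075 | +8.6 |
| 30% / 50% | −0.10 | −11.8 | −0.05 | −5.4 |

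Type I error for 50%/30%, h = 0.5, SD 0.3, with shares fixed at those values:
- Variance seen by the test = 0.09 + 0.25 × (0.25 + 0.21)/2 = 0.1475.
- Its SE = √(0.1475 × 2/30) = 0.0992, so the cut-off = 2.00 × 0.0992 = 0.1985.
- True SE = 0.3 × √(2/30) = 0.0775.
- (0.1985 − 0.10)/0.0775 = 1.27, an error of about 10%.

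If shares vary at random around 50% and 30%, simulation gives 16.6% at SD 0.3 and 10.4% at SD 0.5. With deficiency status in the model, bias is about 0 and error 4.8-5.7%.

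**Case B: PpIX analysed in stratum-matched pairs, with no pair or 25OH-D3 term.** pC = pT, so the between-stratum bias is 0. The test still counts between-stratum variance that matching has removed from the contrast. With half the patients deficient and h = 0.5:
- SD 0.3: variance seen = 0.09 + 0.0625 = 0.1525; SE = 0.1008; cut-off = 0.2018; true SE = 0.0775. Type I: 0.2018/0.0775 = 2.61, about 1%. Power: (0.25 − 0.2018)/0.0775 = 0.62, about 73%. Using the pairs: noncentrality 0.25/0.0775 = 3.23 on 29 df, about 88%.
- SD 0.5: variance seen = 0.25 + 0.0625 = 0.3125; SE = 0.1443; cut-off = 0.2889; true SE = 0.1291. Type I: 2.24, about 2.5%. Power: (0.25 − 0.2889)/0.1291 = −0.30, about 38%. Using the pairs: 0.25/0.1291 = 1.94, about 46%.

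With h = 0.25 and SD 0.3: variance seen = 0.09 + 0.0156 = 0.1056; SE = 0.0839; cut-off = 0.168. Type I: 0.168/0.0775 = 2.17, about 3%. Power: (0.25 − 0.168)/0.0775 = 1.06, about 86%, against 88%. The loss nearly vanishes.

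**The case against.** The strongest reply is that matching already deals with this. A reader of Section 14.0 alone might infer that 25OH-D3 matching serves only the primary outcome and that the PpIX contrast is therefore confounded. Sections 1.7 and 2.1 do not support that: matching is stated for each patient and for the aim that holds the PpIX question. If it is carried through to PpIX, imbalances of 10 to 30 points in deficiency cannot arise in the analysed set. This stands, and it makes Case A a conditional risk. It does not close the point: the secondary-endpoint paragraph never says that the matched set is used, and Case B shows a cost even when it is.

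Second, the list of initial parameters is open and could take in 25OH-D3. True, but it is exploratory and the variable is not named, so the choice would be left until after the data are seen. The random effects for the data hierarchy could likewise be read to include pairs, but the levels named are lesions and repeated measurements.

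Third, the size rests on mice. Section 10.1 sets the human threshold at 20 ng/mL and calls 10-19 ng/mL moderately deficient, so a halving for everyone below 20 is an upper value. This stands. The nearest planning figure is the 0.1 correlation assumed for clearance in matched pairs. If it applied to PpIX, removing 10% of the variance would raise 80% power only to about 84% (2.80/√0.9 = 2.95; 2.95 − 1.96 = 0.99).

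Fourth, PpIX is labelled exploratory in the Protocol Summary and secondary in Sections 12.2.2 and 14.0. That lowers the weight of the point.

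**Conclusion.** The omission is real: as written, the PpIX model has no 25OH-D3 term and no pair term, and its analysis set is undefined. The consequence depends on that set. Outside the matched set the contrast can be biased in either direction, by up to 0.05 of normal PpIX per 10-point difference in deficient share (0.025 if deficiency lowers PpIX by 25%). Inside it there is no between-stratum bias, only a conservative test with lower power: about 15 points lost at SD 0.3 and 8 at SD 0.5 under the upper-value assumption, and much less if the human relation is weaker. Deficient shares, PpIX SDs and the 0.25 gain are assumptions.

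Two stronger readings should be avoided. One is that a 20-point imbalance takes the error rate to about 25%. That needs 0.3 to be the total SD; with 50% and 30% deficient, deficiency alone contributes variance of about 0.0575, leaving a within-stratum SD of √(0.09 − 0.0575) = 0.18. With 0.3 as the within-stratum SD the error is 10-17%, and only outside the matched set. The other is that D3 is expected to help deficient patients more, so that an interaction belongs in the main model. Section 1.5 reports the same benefit in both groups after the longer course, and Section 3.1 aims at equivalent benefit.

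**What to change.** In the secondary-objectives part of Section 14.0:

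1. State that PpIX is analysed in the 25OH-D3-matched set defined for the primary objective.
2. Give the PpIX model continuous baseline 25OH-D3 as a fixed covariate and a matched-pair random effect, alongside the patient and lesion effects.
3. Report a therapy-by-stratum term as exploratory only, in parallel with the ANOVA for clearance. Note that in the D3 group stratum is tied to course length, so the two cannot be separated.
4. Replace the randomization wording, which does not apply to this design.

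No new 25OH-D3 measurement is needed: it is drawn at Visit 1, and controls must have it in order to be matched. The documents do not say whether the controls have comparable PpIX readings, so the section should confirm this. The cost is wording and one or two degrees of freedom. The gain will be small if 25OH-D3 is only weakly related to PpIX in humans, for which the documents give no figure.
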